### **21.3. Analysis Populations**

Patient inclusion into each population will be determined prior to the final analysis. In general:

#### Safety Population:

The Safety Population will consist of all patients who received any amount of study drug. The Safety Population will be used for the summaries of all safety assessments as well as efficacy/biomarker outcomes.

#### Full Analysis Set Population:

The Full Analysis Set (FAS) Population is defined as all randomized patients who received at least one dose of double-blinded study medication and had at least one post-baseline efficacy assessment. All efficacy endpoints will be assessed using this population.

#### Pharmacokinetic Population:

The Pharmacokinetic Population (PP) is defined as all patients who receive the double-blinded study medication and for whom an evaluable concentration-time profile is available for the determination of at least one PK parameter. Patients with emesis after consuming study medication will be assessed on a case-by-case basis for eligibility for inclusion in the PK population. In general, patients who vomit after at least 2 half-lives of the given medication will be included in the PK population (as  $C_{max}$  will presumably be reached by that time).

#### Fibrotic and Inflammatory Biomarker Population:

The Fibrotic and Inflammatory Biomarker Population is defined as all patients who receive the double-blinded study medication and provide biomarker and lymphedema assessment data.

### **21.4. Safety and Tolerability**

All safety assessments, including prior and concomitant medications, AEs, laboratory evaluations, vital signs, ECGs, and other safety assessments will be analyzed using the Safety Population. Data for all endpoints will be tabulated, displayed graphically, or summarized descriptively, as appropriate. Statistical analyses will be descriptive only, no inferential testing will be performed.

#### **21.4.1. Prior and Concomitant Medication**

Prior and concomitant medications will be coded using the most current version of the WHO drug dictionary. Prior and concomitant medications will be listed by patient and summarized by treatment using ATC and PT.

#### **21.4.2. Adverse Events**

AEs will be coded using the MedDRA® version 23.0. A by patient AE data listing, including verbatim term, PT, system organ class (SOC), treatment, severity, and relationship to study drug will be provided. The number of patients experiencing TEAEs and the number of individual TEAEs will be provided by treatment as well as by SOC and PT. The severity and the relationship to study drug of TEAEs will be summarized by treatment.

### **21.4.3. Laboratory Evaluations**

Laboratory evaluations (including hematology, serum chemistry, coagulation, and urinalysis) will be listed and summarized by treatment and by protocol specified collection time point. This will be done both for actual observed laboratory values and for changes from baseline.

The abnormal urinalysis results (dipstick and microscopy), if applicable, will be listed only.

### **21.4.4. Vital Signs**

Vital signs will be listed and summarized by treatment and by protocol specified collection time point. This will be done both for actual observed vital sign values and for changes from baseline.

### **21.4.5. Electrocardiogram Values and Results**

ECG values will be listed and summarized by treatment and by protocol specified collection time point. This will be done both for actual observed ECG values and for changes from baseline.

### **21.4.6. Other Safety Assessments**

Findings of the following assessments will be listed by patient:

- Medical history
- Pregnancy test/FSH test
- Urine drug screen (including Cotinine Test)/ alcohol breath test
- Physical examination
- Serology (HIV, Hepatitis B and C screen)

## **21.5. Pharmacokinetics**

Sparse PK sampling will be employed for population PK analysis (as a secondary endpoint) to determine the variability of LYT-100 drug concentration data from individual patients across multiple clinical sites.

PK parameter values will be listed and summarized by treatment and assessment time point.

## **21.6. Fibrotic and Inflammatory Biomarkers**

The association between fibrotic and inflammatory biomarkers (in particular TGF- $\beta$ 1), and disease progression in mild to moderate lymphedema will be examined.

Exploratory analysis of fibrotic and inflammatory biomarkers include: G-CSF, MIG, FGF-2, IL-4, IL-10, lymphotoxin  $\alpha$ /TNF- $\beta$ , leptin, IL-6, IL-1 $\beta$ , TNF- $\alpha$ , TGF- $\beta$ 1, MMP-9, TIMP-1, and MCP-1.

For each biomarker of interest, scatterplots of the recorded biomarker value against each of the disease progression metrics (limb water content, limb volume, TDC, tissue firmness, and visual analog scales; see Section 17 and Section 21.7) will be provided on a single set of axes, (with color used to identify the different disease progression metrics). All patients and all time points at which both biomarker assessment and disease progression assessment are performed will be included on the one plot. This will be repeated considering the change from baseline in the

biomarker values as opposed to actual observed values. Further details of this exploratory biomarker analysis will be provided in the SAP.

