PureTech LYT 100, Inc. intends to study LYT-100 for the treatment of lymphedema, a chronic condition that is characterized by swelling due to the build-up of lymph fluid and tissue fibrotic remodeling. Lymphedema is a progressive fibrotic and inflammatory disease, and there is no approved pharmacologic therapy for lymphedema. LYT-100 has both anti-fibrotic and anti-inflammatory activity based on *in vitro* and *in vivo* models of fibrotic and inflammatory conditions. Existing treatments focus on reducing the symptoms and using mechanical compression to prevent swelling. However, these treatments do not address the underlying mechanisms of lymphedema and are required chronically for management of the condition. Millions of people worldwide are affected by secondary lymphedema (Rockson et al., 2019), and each year up to 15% of cancer survivors with malignancies ranging from melanoma to sarcoma will develop lymphedema (Cormier et al., 2010). As such, there is an unmet medical need for developing safe and effective new treatments for lymphedema.

The purpose of this study is to evaluate the safety, tolerability, PK, and effect on secondary clinical endpoints of LYT-100 administered twice daily (BID) for 6 months in breast carcinoma patients with secondary lymphedema following axillary node dissection and/or sentinel lymph node biopsy, with or without radiation.

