#### *Secondary Objectives*

- To explore efficacy signals of LYT-100 on:
  - Lymphatic obstruction and subsequent edema,
  - Infection (as characterized by cellulitis and/or lymphangitis), and
  - QoL.
- To assess the population PK profile of the double-blinded study medication
  - To describe the association between fibrotic and inflammatory biomarkers, in particular: TGF- $\beta$ 1, and disease progression in mild to moderate lymphedema.

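### The Section 21.6 biomarker plots mix LYT-100 and placebo patients at all visits without identifying arm or patient, so a drug effect can create or dilute the association they are meant to show

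*Combined protocol and SAP*

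**What the plan says.** The secondary objective in Section 8.1 is "To describe the association between fibrotic and inflammatory biomarkers" (TGF-β1 in particular) and disease progression. Section 21.6 repeats the target: the association with "disease progression in mild to moderate lymphedema will be examined". Neither place mentions treatment.

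Section 21.6 then gives the analysis. For each biomarker, the value is plotted against the progression metrics ("limb water content, limb volume, TDC, tissue firmness, and visual analog scales") on a single set of axes, "with color used to identify the different disease progression metrics". The plot includes "All patients and all time points at which both biomarker assessment and disease progression assessment are performed". A second version follows: "This will be repeated considering the change from baseline in the" biomarker values. No symbol, panel, line or model term for arm, visit or patient is named. Further details are left to the SAP.

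The biomarker population in Section 21.3 includes both arms. Elsewhere, Section 21 is organized by arm: adverse events, laboratory values, vital signs, ECGs and PK parameters are all summarized by treatment.

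**The concern.** Treatment is a possible common cause of both axes. The Introduction (Section 7.1) states that "LYT-100 has both anti-fibrotic and anti-inflammatory activity based on" in vitro and in vivo models, so the drug acts on the biology behind the biomarkers. The trial itself explores whether the drug moves the progression metrics. When treated and untreated points share one unlabelled cloud, the pattern combines two things: how biomarker and disease vary together at a given treatment status, and how far the drug displaces each of them. A reader of the plot cannot separate the two.

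The repeated points add to this. Each patient can contribute five points per metric with nothing linking them, so differences between patients and movement within a patient look the same.

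The study is described as hypothesis-generating, so these plots are themselves the output for this objective. No test or model is specified behind them that would correct a misleading picture.

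**Working it through.** The plan states no correlation, power or error rate for this analysis, so there is no figure to reproduce. The check asks how far pooling could distort the picture.

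**Inputs from the documents**
- About 50 patients, 1:1, so 25 per arm (Section 21.1, Table 4).
- Biomarker samples at Day -1 and Weeks 1, 8, 16 and 26, which is five (Table 5; Table 11 also counts five).
- Four physical metrics plus four visual analog scales, so eight series per plot.

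**Counts, assuming no dropout**
- Points per metric: 50 × 5 = 250.
- Points on LYT-100: 25 × 4 = 100, a share p = 100/250 = 0.40.
- Points per plot over eight series: 250 × 8 = 2,000.

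**Assumptions not in the documents.** The drug shifts the biomarker by dx and the metric by dy, in SD units at fixed treatment status. ρ is the correlation at fixed treatment status.

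**Formula.** With c = p(1 − p) = 0.40 × 0.60 = 0.24,

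r(pooled) = (ρ + c·dx·dy) / √[(1 + c·dx²)(1 + c·dy²)].

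**Shift on both axes, ρ = 0, dx = dy = d**, so r = 0.24d² / (1 + 0.24d²):
- d = 0.5: 0.06/1.06 = 0.057
- d = 0.8: 0.1536/1.1536 = 0.133
- d = 1.0: 0.24/1.24 = 0.194

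**Shift on one axis only**, so r = ρ/√(1 + 0.24d²):
- ρ = 0.40, d = 1: 0.40/√1.24 = 0.359
- ρ = 0: r stays 0. A one-axis effect can dilute an association but cannot create one.

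**Simulation check** (25 per arm, five visits, within-patient correlation 0.6, 3,000 runs, ρ = 0, 1 SD on both axes):
- Constant effect from Week 1: pooled r = 0.19, matching the formula.
- Effect rising linearly to 1 SD at Week 26: pooled r = 0.10.
- Computed within arm and visit, or in placebo alone: 0.00 in both cases.

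**Change-from-baseline plots.** Section 21.6 puts the biomarker on the change scale but does not say that the metric follows, so no figure is given for that plot as written. If both axes were changes, the same simulation gives 0.24 for a constant 1 SD effect and 0.14 for the ramp.

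**What panels alone leave.** The LYT-100 panel of observed values still holds 25 pre-dose and 100 on-drug points. There p = 100/125 = 0.80 and c = 0.16, so with ρ = 0 and a constant 1 SD shift on both axes r = 0.16/1.16 = 0.14. Joining each patient's points from Day -1 makes that displacement visible. The placebo panel is free of it.

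**The case against.** The strongest reply is that Section 21.6 is openly a summary. It defers further details to the SAP, and Section 21.2 lets the SAP supersede the protocol. Using color for the metric does not forbid symbols or panels for arm. This stands in part: if the SAP already separates the arms, confirming that closes the point. But the section does state a rule, that everyone and every paired visit go on one plot, and a deferral of further details does not reverse it.

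Second, the size may be small. No correlation coefficient is planned, the 0.19 needs a full 1 SD shift on both axes from Week 1, and the stated drug activity comes from in vitro and in vivo models, not from shifts of that size in these patients. This stands. Sampling noise is also larger than the dilution. With within-patient correlation 0.6 on both axes, 250 points carry about 250/(1 + 4 × 0.36) = 102 effective observations, a standard error near 1/√102 = 0.10, against a loss of 0.04 from 0.40.

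Third, other planned output helps. Section 21 plans standardized differences between arms for efficacy and other endpoints as the data warrant, and the Synopsis plans change from baseline for every biomarker and metric. A reader could learn from these whether the drug moved both axes, but could not remove that movement from the plot.

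Fourth, the work is exploratory, with no hypothesis testing. So no error rate, efficacy comparison or safety decision depends on it. That limits the consequence; it does not make the pooled plot interpretable.

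**Conclusion.** The point holds as a weakness in how the figures are specified. The direction is certain: a shift on both axes can create an association and a shift on one axis can only dilute one. The size is unknown because the documents give no effect sizes. Under the assumptions above it is slight at 0.5 SD or below (at most about 0.06 created) and becomes noticeable near 1 SD on both axes (0.10 to 0.19, depending on how quickly the effect appears).

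Two stronger readings are not supported. A reader might infer that the plan will present the pooled association as the untreated course of the disease. The documents speak only of disease progression in mild to moderate lymphedema, and describing on-treatment movement is legitimate in a study of this kind.

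A reader might also infer that the objective should rest only on baseline samples plus placebo follow-up, which is 50 + 100 = 150 of the 250 points. Nothing in the documents requires that, and the trade is debatable. The 25 placebo patients give 125/2.44 = 51 effective observations and the 25 LYT-100 baselines add 25, about 76 in all, for a standard error near 0.115 instead of 0.10. At a 0.5 SD shift, the precision lost roughly offsets the bias removed. Showing arm deals with the problem without discarding data.

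**What to change.** In Section 21.6, or in the SAP figure specification:

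- Draw each biomarker plot, for observed values and for change from baseline, in separate LYT-100 and placebo panels on common axes.
- Join each patient's points in visit order, so that in the LYT-100 panel movement away from the pre-dose value can be seen.
- State that the biomarker-progression association will be described within arm, not from the pooled cloud.
- Keep all patients and all paired visits.

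The cost is a revised figure specification and a sentence of text. No new samples, visits or patients are needed.

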#### *Study-Specific Requirements*

Analysis of clinical assessments and potential progression or disease will be explored. Comparisons between LYT-100 and placebo will be based on clinical interpretation of effect, magnitudes of effect, and a preponderance of evidence. Estimates of changes over time from these data may be used to power future clinical studies.

The primary endpoints are safety (clinical laboratory parameters, vital signs, ECGs, and spontaneously reported AEs) and tolerability of the double-blinded study medication. Secondary endpoints include efficacy (lymphedema assessments, infection, and health-related QoL), population PK, and fibrotic and inflammatory biomarkers of the double-blinded study medication.

Change from baseline to each post-baseline visit (through Week 26; on-treatment effect) on the following endpoints will be calculated for the following endpoints: fibrotic and inflammatory biomarkers (G-CSF, MIG, FGF-2, IL-4, IL-10, lymphotoxin  $\alpha$ /TNF- $\beta$ , leptin, IL-6, IL-1 $\beta$ , TNF- $\alpha$ , TGF- $\beta$ 1, MMP-9, TIMP-1, MCP-1), limb water content (BIS), limb volume (truncated cone tape measure and/or perometry), tissue dielectric constant (MoistureMeterD), tissue firmness (tonometry/SkinFibroMeter), visual analog scales (pain, swelling, discomfort, and function), and QoL (LYMPH-Q, LYMQOL). For select efficacy outcomes, use of a mixed model for repeated measures (MMRM) will be used to provide model-based estimates of changes over time in each of these outcomes. Descriptive statistics will also be provided at each time point. Details for the model (including covariates to be included) will be provided in the SAP.

Data for all endpoints will be tabulated, displayed graphically, or summarized descriptively, as appropriate. No formal hypothesis testing will be performed.

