### **21.2. General Statistical Plan**

Statistical methods will be further outlined in an SAP and approved by the Sponsor prior to any analysis. Procedures outlined in the SAP will supersede protocol specified statistical methods in the event of divergence.

The baseline value for all variables will be the last measurement obtained prior to the patient receiving the first dose of study treatment.

Patient disposition (including the number and percent of patients who are enrolled, who receive treatment, who prematurely discontinue and reasons for discontinuation, and who complete the study) will be tabulated by treatment group. Summary statistics for days of exposure and concentration of exposure will be provided by treatment group.

AEs, concomitant medications, clinical laboratory findings, physical examinations, ECGs, and vital signs for each patient will be listed and also summarized in tabular form, as appropriate.

Demographic information will be listed for each patient and summarized. TEAEs and laboratory, vital signs, and ECG parameters will be summarized. In addition, change from baseline will be summarized for laboratory and vital sign parameters. Shift tables will also be provided for clinical laboratory results. ECG results will be classified as normal and abnormal and summarized. ECG results for QTcF will also be classified as < 450 msec, 450 to 500 msec or > 500 msec. Changes in physical exams will be described in the final study report.

In general, descriptive statistics (arithmetic mean, standard deviation [SD], median, minimum, and maximum) will be calculated for continuous valued safety data by specified assessment time point. Frequency summaries (i.e., number and percentage of each observed category) will be provided for categorical and ordinal safety data by treatment and by specified assessment time point.

No formal hypothesis testing will be performed for this study.

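### As worded, section 21.6 plots biomarker change against the level of each disease metric and never against its change; change-against-change panels would serve the progression objective better at little cost.

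*Combined protocol and SAP*

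**What the plan says.** Section 21.6 describes two displays for each biomarker.

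- The first plots the observed biomarker value against the disease metrics: limb water content, limb volume, tissue dielectric constant (TDC), tissue firmness and the visual analog scales (VAS). The metrics "will be provided on a single set of axes, (with color used to identify the different disease progression metrics").
- The second is the same plot with one alteration: "This will be repeated considering the change from baseline in the" "biomarker values as opposed to actual observed values".

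On the data included: "All patients and all time points at which both biomarker assessment and disease progression assessment are performed will be included on the one plot". The metrics carry a cross-reference ("see Section 17 and Section 21.7"), and the section closes: "Further details of this exploratory biomarker analysis will be provided in the SAP". Section 21.2 adds: "Procedures outlined in the SAP will supersede protocol specified statistical methods in the event of divergence". No SAP text accompanies the protocol.

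Other sections bear on this. The secondary objective in 8.1 asks how the biomarkers, TGF-β1 above all, relate to progression of the disease. Section 17 generally assesses efficacy through change from baseline. The synopsis, under Study-Specific Requirements, says: "Change from baseline to each post-baseline visit (through Week 26; on-treatment effect) on the following endpoints will be calculated". Its list covers all 14 biomarkers and every metric named in 21.6.

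**The concern.** Progression is a change within a patient. Read literally, the first display sets level against level and the second sets biomarker change against metric level. Neither shows whether patients whose biomarker moved also had disease that moved. These scatterplots are the only method the protocol names for this association, so no other stated analysis fills the gap.

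The two displays can mislead in different ways. Change against level can make a link between changes look weaker than it is. Level against level mixes differences between patients with movement within patients, so it can show a link when no within-patient link exists.

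Two layout choices add to this. Metrics on very different scales share one axis. Both arms and repeated visits are pooled, colour is taken up by the metric, and no marking of arm or patient is described. A treatment effect on both variables could then look like a biomarker–disease association.

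**Working it through.** The protocol gives no correlation, variance or target precision for this analysis, so there is no figure to reproduce. The variances, correlations and treatment effects below are assumptions. The r values stand for what the eye would see, since no coefficient is planned.

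**Counts from the documents.** Table 5 has biomarkers at Day -1 and Weeks 1, 8, 16 and 26, which matches the 5 samples in Table 11. The metrics are measured at all of these visits, so there are 5 common visits. With about 50 patients and 8 metrics (four VAS counted separately):

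- Level plot: 8 × 50 × 5 = 2,000 points. With VAS as one metric: 5 × 50 × 5 = 1,250.
- Change plot, post-baseline: 8 × 50 × 4 = 1,600, or 5 × 50 × 4 = 1,000. If baseline visits are kept, a further 8 × 50 = 400 (or 5 × 50 = 250) points have biomarker change zero by definition.

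**Change against level.** Let s be the stable share of the variance. In the first two models below it equals the baseline-to-follow-up correlation. In the two drift models it is the part of Week 26 variance already present at baseline. The table gives the change-against-level correlation divided by the change-against-change correlation. Simulations used 50 patients, the five visits, true r of 0.3, 0.5 and 0.7, and 2,000 replicates per cell.

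| Model | s = 0.5 | s = 0.7 | s = 0.9 |
|---|---|---|---|
| Independent visit errors, √((1−s)/2) | 0.500 | 0.387 | 0.224 |
| Same, simulated | 0.505–0.510 | 0.389–0.394 | 0.220–0.231 |
| Biomarker change unrelated to baseline metric, √(2(1−s)) | 1.000 | 0.775 | 0.447 |
| Same, simulated | 0.996–1.007 | 0.774–0.780 | 0.452–0.457 |
| Random walk, simulated | 0.571–0.581 | 0.407–0.420 | 0.219–0.238 |
| Random slope, simulated | 0.515–0.526 | 0.370–0.377 | 0.186–0.210 |

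A true 0.50 therefore shows as 0.25–0.50, 0.18–0.39 and 0.09–0.23 at the three shares.

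**Level against level.** Apparent r = s × r(between) + (1−s) × r(within), for s = 0.5 / 0.7 / 0.9:

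- both 0.5: 0.50 / 0.50 / 0.50 (no loss)
- within 0.5, between 0: 0.25 / 0.15 / 0.05
- within 0, between 0.5: 0.25 / 0.35 / 0.45

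Simulation agrees to within about 0.01.

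**Arms pooled, treatment effect only.** Take an effect of d on both variables, in units of the SD of a level, and no association within arm. For change against change, r = (d²/4) / (2(1−s) + d²/4). At s = 0.7 and d = 0.5 this is 0.0625/0.6625 = 0.094 (simulated 0.096). At d = 1 it is 0.25/0.85 = 0.294 (simulated 0.295). Simulated values for d = 0.5 and d = 1:

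| s | Level–level | Change–level | Change–change |
|---|---|---|---|
| 0.5 | 0.057, 0.198 | 0.056, 0.200 | 0.059, 0.198 |
| 0.7 | 0.058, 0.192 | 0.076, 0.246 | 0.096, 0.295 |
| 0.9 | 0.058, 0.194 | 0.117, 0.336 | 0.240, 0.558 |

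Within arm and visit, the change–change correlation was −0.002 to 0.002, so marking the arm lets the reader see the artefact.

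**Shared axis.** Section 17 puts VAS on 0–10 and TDC on 0–100%. In raw units, an axis running to 100 gives the whole VAS range 10/100 = 10% of its length and one VAS point 1%. If TDC values ended at 60 or 40 (assumed), the VAS range would fill 10/60 = 17% or 10/40 = 25%.

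**The case against.** The strongest reply is that section 21 is only a summary. Section 21.6 defers detail to the SAP, which prevails over the protocol, and panels, scaling and symbols are normally settled there. The cross-reference to section 17, which works in changes, may mean that the metrics were always intended as changes. This is possible but not the likelier reading: 21.6 switches only the biomarker, and it includes every common visit and therefore baseline.

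The second reply is that little depends on these plots. The study is hypothesis-generating, and section 14.2 says that methods for biomarkers other than TGF-β1 will not be validated. The objective does not ask for association by arm. All of that is true and limits the weight of the point.

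The third reply concerns the numbers. The stable share does not mean the same thing in all four models. The result runs from no loss (ratio 1.00) to a loss of 81% (1 − 0.186), and nothing in the documents selects among these. At s = 0.9 the SD of a change is √(2 × 0.1) = 0.45 level SDs, so a 1 SD effect is 1/0.45 = 2.2 change SDs, which is very large. The axis figures assume unstandardised units, on which 21.6 is silent. These points stand: the figures show what could happen, not what will.

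The fourth reply is that the proposed panels carry the same hazard. Treatment alone produces at least as strong an apparent correlation there as in the change-against-level plot (0.240 against 0.117 at s = 0.9 and 0.5 SD). Change scores also carry two measurement errors, and a patient's changes share one baseline. This is correct, and it is why arm marking and joined points are part of the remedy.

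**Conclusion.** The point holds. As worded, 21.6 never pairs biomarker change with disease change, although the objective concerns progression and the protocol already calculates every change needed. This goes beyond missing detail, because following the stated displays would give a poorer view of the only association analysis named.

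The size cannot be fixed from the documents. Under the assumed models, the second display shows between 19% and 100% of the true change-to-change correlation. The first display loses nothing when within- and between-patient correlations agree, and otherwise can understate or invent a within-patient link. Pooling the arms matters little at a 0.5 SD effect in the planned plots (r of about 0.06–0.12) and more at 1 SD (about 0.19–0.34).

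No test, sample size or primary conclusion is affected. It is a minor to moderate improvement to an exploratory, descriptive analysis. It should be made before analysis, unless the SAP has already done so.

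**What to change.** In the SAP, starting with TGF-β1, which section 14.1.2 singles out:

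- Add plots of biomarker change from baseline against change from baseline in each disease metric, with one panel per metric on its own scale.
- Mark the arm and join each patient's points. Arm marking is essential here: treatment alone would show in these panels as r = 0.06–0.24 at 0.5 SD and 0.20–0.56 at 1 SD (s from 0.5 to 0.9).
- Keep the two planned displays if wanted.
- If 21.6 already intends change in the metrics, say so in one sentence.
- Optionally, give a descriptive within-patient association estimate with a confidence interval and no test, with and without adjustment for arm, because joint movement caused by treatment may itself be of interest.

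The cost is some programming and more figures: 8 panels for TGF-β1 (5 if VAS counts as one metric) and up to 8 × 14 = 112 for all biomarkers, with up to 50 × 4 = 200 points per panel. No new data are required.
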